8.4. Examination of Subgroups

Subgroup analyses of the primary and two secondary (ACQ-5 score and pre-bronchodilator FEV₁) efficacy endpoints will be performed for all of the subgroups specified below. In addition, subgroup analyses of the secondary efficacy endpoint of annualized rate of severe asthma exacerbations will also be performed for select subgroups as specified below. For any subgroup level that does not comprise $\geq 10\%$ of the ITT population, the analyses based on the models will not be performed. The subgroups of interest are described below.

Demographic and general baseline characteristic subgroups:

- Age (years; $< 65, \ge 65$)
- Sex (male, female)
- BMI (kg/m²; < 30, \geq 30)
- Baseline ICS dose ([per randomization and per actual value]; medium, high, including comparison of GB001 medium to Placebo high)
- Region (North America, Eastern Europe, Western Europe)
- Total number of exacerbations in the past 12 months (1, > 1)

Efficacy-related baseline characteristic subgroups:

- Pre-bronchodilator percent predicted FEV₁ at Screening (%; $< 60, \ge 60$)
- ACQ-5 score at Baseline ($< 1.5, \ge 1.5$)

Biomarker baseline characteristic subgroups:

- Blood eosinophils at Baseline (GI/L; < 0.20, ≥ 0.20; < 0.25, ≥ 0.25 [including for annualized rate of severe asthma exacerbations]; < 0.30, ≥ 0.30)
- FeNO at Baseline (ppb; < 25, ≥ 25 [including for annualized rate of severe asthma exacerbations]; < 30, ≥ 30; < 35, ≥ 35; < 50, ≥ 50)
- Blood eosinophils and FeNO at Baseline ([blood eosinophils < 0.25 GI/L and FeNO < 25 FeNO ppb] vs [blood eosinophils ≥ 0.25 GI/L and/or FeNO ≥ 25 ppb] {including for annualized rate of severe asthma exacerbations}; repeat for 0.25 vs 30, 0.25 vs 35, and 0.25 vs 50)
- Blood eosinophils and FeNO at Baseline ([blood eosinophils < 0.25 GI/L and FeNO < 25 FeNO ppb] vs [blood eosinophils < 0.25 GI/L and FeNO ≥ 25 ppb] vs [blood eosinophils ≥ 0.25 GI/L and FeNO < 25 ppb] vs [blood eosinophils ≥ 0.25 GI/L and FeNO < 25 ppb] vs [blood eosinophils ≥ 0.25 GI/L and FeNO < 25 ppb] vs [blood eosinophils ≥ 0.25 GI/L and FeNO > 25 ppb]; including for annualized rate of severe asthma exacerbations)
- IgE (IU/mL; normal [≤ 158], high [> 158])
- 25-Hydroxyvitamin D at Baseline $(ng/mL; \leq 20, > 20)$
- Chloride at Baseline (mmol/L; ≤ Quartile 1, > Quartile 1-≤ Quartile 2, > Quartile 3-≤ Quartile 3, > Quartile 3, where quartiles are based on the ITT population)

Models used for the subgroup analyses will be the same as those used for the primary and secondary efficacy endpoints as specified in Section 8.3.1 and Section 8.3.2.1 with covariates for the subgroup (if different than the aforementioned covariates i.e. baseline ICS dose (medium or high) at randomization and region; for the efficacy-related baseline characteristic subgroups, baseline pre-bronchodilator FEV_1 or baseline ACQ-5 score will be replaced with a categorical subgroup variable) and treatment group by subgroup interaction added. If the model does not converge, a reduced model including only treatment group, ICS dose at randomization, and region will be used.

Heterogeneity of treatment effect across different levels of each subgroup will be evaluated by presenting p-values for the treatment by subgroup interaction. The interaction term tests whether the treatment effect is significantly different across different levels of the subgroup, between males and females, for example. If a subgroup variable has more than two levels then the least severe level (where applicable) will be used as the reference subgroup, and the test will assess whether the treatment effect in the more severe levels differs from that in the reference subgroup.

Forest plots of the treatment effect estimates and corresponding 95% CIs from the subgroup analyses will be provided.

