4.1.1. Study Design

The study will commence with a Screening visit (Visit 1), at which informed consent will be obtained and inclusion and exclusion criteria will be assessed. Informed consent may be obtained prior to the day of the Screening visit to allow for medication washouts or for other logistical reasons such as obtaining documentation of exacerbations or historical reversibility, if necessary. All other screening procedures should be completed on the day of the Screening visit. Subjects not meeting the eligibility criteria will be deemed screen failures and will not continue participation in the study (see [Section 5.4](#)). Eligible subjects will enter a Run-in period of a minimum of 2 weeks and a maximum of 6 weeks and will remain on their SOC regimen. The Run-in period commences with completion of all Screening visit procedures and concludes at the Randomization visit. During the Run-in period, subjects will capture PEF and asthma symptoms in an eDiary daily. Subjects who experience an asthma exacerbation during the Run-in period will receive appropriate treatment and remain in the Run-in period until their asthma status has returned to baseline status for at least 1 week. Subjects who are not able/eligible to be randomized due to ongoing asthma exacerbation at the end of the Run-in period will be discontinued from study participation and be labeled as Run-in failures. Subjects will remain on their SOC therapy during the Run-in period.

At Visit 2 (Week 0, Day 1), subjects who meet the randomization eligibility criteria will be randomized in a 1:1:1:1 ratio to receive one of the following double-blind treatments for 24 weeks:

- GB001 60 mg daily
- GB001 40 mg daily
- GB001 20 mg daily
- Matching placebo daily

Randomization will be stratified by baseline ICS dose (medium or high, as defined in Appendix 10; [Section 10.10](#)) and country.

The first dose of double-blind investigational product (IP) will be administered in the clinic on Day 1. All subsequent doses will be taken orally at home at bedtime on an empty stomach.

Following initiation of IP, subjects will visit the clinic for assessments at Weeks 2, 3, and 4, followed by visits approximately every 4 weeks for an additional 5 visits. Subjects should remain on their stable current SOC therapy (ie, medium or high dose ICS plus additional controller therapy) through the duration of their time on study (refer to Schedule of Activities, [Section 1.3](#)).

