4.2. Scientific Rationale for Study Design

4.2.1. Study Population

The target population is patients with moderate to severe asthma who are currently receiving GINA step 4 or 5 therapy and have evidence of eosinophilic inflammation. Reducing eosinophilic inflammation within the lungs, assessed by measuring sputum eosinophils, has been associated with a reduction in asthma exacerbations (Haldar, 2009; Pavord, 2012). It is anticipated that GB001, as a DP₂ antagonist, will reduce sputum eosinophilia and consequently asthma exacerbations. As measurement of sputum eosinophils is cumbersome and requires sites experienced with this procedure to obtain appropriate samples, a surrogate measure of lung eosinophils, namely peripheral blood eosinophils, will be used in this study. The cut-off threshold of 250 cells/μL has been selected for this study as it is predicted to have a sensitivity of 84% and a specificity of 91% to differentiate less than versus $\geq 3\%$ sputum eosinophils (Wagener, 2015).

Based upon regulatory guidance, patients with a history of asthma exacerbations should be recruited in studies where the primary endpoint is exacerbation reduction (EMA, 2015). Patients with a history of exacerbations are more likely to experience future exacerbations. Therefore, this study will be recruiting subjects with a history of at least 1 asthma exacerbation in the previous 12 months.

In addition, DP₂ antagonists might have an effect in a subset of subjects with inflammation beyond the lower airways such as upper airways and skin. Thus, exploratory assessments targeting these tissues will evaluate additional beneficial effects as a result of treatment with GB001.

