5.1. Inclusion Criteria

To confirm eligibility, a review of each subject's medical records should be performed prior to the subject entering the Run-in period. Prior to randomization, additional randomization criteria (including blood eosinophils ≥ 250 cells/ μ L; [Section 5.3](#)) must be met.

Subjects are eligible to enter the Run-in period only if all the following criteria are met:

1. **Informed Consent:** Capable of giving signed informed consent which includes compliance with the requirements and restrictions listed in the informed consent form (ICF) and in this protocol.
2. **Age:** ≥ 18 and < 75 years of age at the time of Screening visit.
3. **Gender:** Males or females:
 - a. Women of childbearing potential (WOCBP) must use an acceptable method of contraception (see Appendix 4, [Section 10.4](#)) at least 1 month prior to Screening through 28 days after the last dose of IP.
4. **Weight:** at least 40 kg.
5. **Diagnosis of asthma:** A diagnosis of asthma by a physician according to GINA guidelines of at least 12 months prior to Screening.
6. **ICS plus additional controller:** Subjects with a documented requirement for regular treatment with medium or high dose ICS and at least one other controller medication for at least 12 months prior to Visit 1. Subjects must maintain a stable ICS dose regimen during the 4 weeks prior to Visit 1.
 - a. Medium dose ICS is defined as an ICS dose equivalent to fluticasone propionate > 250 to 500 mcg/day and high dose is defined as an ICS dose equivalent to fluticasone propionate > 500 mcg/day (for equivalent ICS doses see Appendix 10, [Section 10.10](#))
 - b. An additional controller medication such as LABA, long-acting muscarinic antagonist (LAMA), or leukotriene receptor antagonist (LTRA).
7. **FEV₁:** a pre-bronchodilator FEV₁ of $\leq 85\%$ of predicted normal.
8. **Reversibility/Airway Hyperresponsiveness:**
 - At least 12% in FEV₁ following 4 puffs of albuterol 400 μ g ex-US (360 μ g US) or 1 equivalent nebulized dose/salbutamol 100 mcg at Screening. Reversibility is to be assessed in all subjects at Screening.
 - If a subject does not reverse at least 12% at Screening, the site may submit historical documentation of one of the following for review and approval by the Medical Monitor:
 - reversibility in the 24 months prior to Screening visit, **OR**

- airway hyperresponsiveness demonstrated by a positive methacholine, histamine, or mannitol challenge.

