6.4. Concomitant Therapy

Subjects should remain on their current SOC therapy (ie, medium or high dose ICS plus additional controller therapy) through the duration of their time on study. If a subject experiences asthma worsening as defined in [Section 4.1.1](#) or if a subject discontinues IP or withdraws from the study due to lack of efficacy, SOC therapy may be adjusted, as needed, at the discretion of the Investigator.

Any medication or vaccine (including over-the-counter or prescription medicines, vitamins, and/or herbal supplements) that the subject is receiving at the time of enrollment or receives during the study must be recorded along with:

- Reason for use
- Dates of administration including start and end dates
- Dosage information including dose and frequency

The Medical Monitor should be contacted if there are any questions regarding concomitant or prior therapy.

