2.4. Randomization and Treatment Regimens

This study will randomize approximately 480 subjects, with approximately 120 subjects per treatment group, randomized in a 1:1:1:1 ratio to the following treatment groups:

- GB001 60 mg daily
- GB001 40 mg daily
- GB001 20 mg daily
- Matching placebo daily

Randomization will be stratified by baseline ICS dose (medium or high, as defined in Protocol Section 10.10) and country.

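### SAP 8.4 places a non-randomized contrast, GB001 on medium-dose ICS against placebo on high-dose ICS, among the subgroup treatment effects without labelling it as such

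*SAP*

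**What the plan says.** SAP 8.4 lists baseline ICS dose, both as recorded at randomization and as actually taken, among the subgroups for the primary endpoint and for change in ACQ-5 and pre-bronchodilator FEV1. To the medium and high levels it adds "including comparison of GB001 medium to Placebo high". ICS dose is not flagged for the exacerbation-rate subgroup analyses, so the contrast does not extend to that endpoint.

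Three places fix the status of ICS dose:

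- Protocol 5.1 makes it an entry requirement: "Subjects with a documented requirement for regular treatment with medium or high dose ICS and at least one other controller medication".
- Protocol 4.1.1 keeps it unchanged during the study: "Subjects should remain on their stable current SOC therapy". Protocol 6.4 repeats this and allows adjustment at the investigator's discretion after worsening or after stopping for lack of efficacy.
- SAP 2.4 uses it only to balance the arms: "Randomization will be stratified by baseline ICS dose (medium or high, as defined in Protocol Section 10.10) and country".

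What the trial assigns is GB001 60, 40 or 20 mg or placebo, "randomized in a 1:1:1:1 ratio to receive one of the following double-blind treatments for 24 weeks" (Protocol 4.1.1).

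For the subgroups, SAP 8.4 reuses the main models with a treatment-by-subgroup interaction. For the primary endpoint, the covariates in SAP 8.3.1 are ICS dose, region, baseline pre-bronchodilator FEV1 and baseline ACQ-5. If the subgroup model does not converge, the reduced model contains only treatment, ICS dose and region. Section 8.4 ends with "Forest plots of the treatment effect estimates and corresponding 95% CIs from the subgroup analyses will be provided". It gives no purpose, estimand or caveat for the crossed contrast.

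**The concern.** Every other ICS-dose comparison in SAP 8.4 sets a GB001 group against placebo within one level of ICS, where stratified randomization protects it. The crossed contrast changes two things at once: the randomized treatment and the background ICS dose. The second change carries with it the reasons for prescribing, any difference in severity, and the effect of the ICS dose itself.

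The population is described as "patients with moderate to severe asthma who are currently receiving GINA step 4 or 5 therapy" (Protocol 4.2.1), so the two strata may well differ in prognosis. Listed without a label beside randomized effects, the result could be read as a GB001 effect, or as evidence that GB001 plus medium-dose ICS does as well as or better than high-dose ICS. An inert drug could produce that result, and a working drug could fail to show it.

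**Working it through.** **The plan's own figure.** The documents give no number for this contrast. The one related figure is the 80% power in SAP 2.5. With 25% and 10.2%, OR = (0.102/0.898)/(0.25/0.75) = 0.341, a 66% reduction in odds. With 120 × 0.92 ≈ 110 evaluable per arm, SE(log OR) = √[1/(110 × 0.25 × 0.75) + 1/(110 × 0.102 × 0.898)] = 0.384. Power = Φ(1.077/0.384 − 1.96) ≈ 0.80. The figure reproduces. It concerns the randomized comparison and says nothing about the crossed one.

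**Decomposition.** Let G and P be GB001 and placebo, M and H medium and high ICS:

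OR(crossed) = odds(G,M)/odds(P,H) = [odds(G,M)/odds(P,M)] × [odds(P,M)/odds(P,H)]

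The first factor is the randomized effect in the medium stratum. The second compares placebo subjects who differ in ICS dose, which nobody randomized. For ACQ-5 and FEV1 the same holds on the additive scale: crossed difference = drug effect in M + (placebo mean in M − placebo mean in H).

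**Size of the distortion.** Let k be the high-versus-medium odds ratio for worsening on placebo. The documents do not give it, so a range is assumed. The second factor is then 1/k. The last column is the chance of a nominal two-sided p < 0.05, in either direction, with no drug effect (unadjusted test, 110 per arm, overall placebo risk 25%, assumed 30 to 70% of subjects on high-dose ICS).

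| k | Crossed OR, drug inert | Crossed OR, true drug OR 0.34 | Chance of p < 0.05, drug inert |
|---|---|---|---|
| 0.67 | 1.49 | 0.51 | 11–15% |
| 1 | 1.00 | 0.34 | 5% |
| 1.5 | 0.67 | 0.23 | 12–15% |
| 2 | 0.50 | 0.17 | 24–34% |
| 3 | 0.33 | 0.11 | 50–67% |

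**Chance of a result favouring GB001.** Assumptions: inert drug, 60 subjects per cell (half of 120, an assumed even split), three doses sharing one placebo-high group, unadjusted pooled two-proportion z-test, counting z < −1.96. By simulation:

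| Risk, medium vs high | Expected OR | One dose | At least one of three |
|---|---|---|---|
| 25% vs 25% | 1.00 | 2.6% | about 6.5% |
| 22% vs 28% | 0.282/0.389 = 0.73 | about 12% | about 25% |
| 20% vs 30% | 0.250/0.429 = 0.58 | about 25% | about 46% |
| 28% vs 22% | 0.389/0.282 = 1.38 | 0.3–0.4% | about 1% |

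The benchmark for one dose is 2.6%. For any of three it is about 6.5%, because part of that column is multiplicity, which SAP 8.1.3 openly leaves unadjusted.

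**Masking.** With a true drug OR of 0.341 and risks of 28% (medium) and 22% (high), the crossed OR is 0.341 × 1.38 = 0.47 and the chance of nominal significance for one dose is about 32%. With both strata at 25% it is about 57%.

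**What the model does.** Region, baseline FEV1 and ACQ-5 absorb the part of the stratum difference that they capture. The rest stays in the ICS coefficient, which is itself a component of the contrast. The reduced model for non-convergence drops FEV1 and ACQ-5, and the interaction as well.

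**The case against.** The strongest reply is that this is one parenthetical in one of many exploratory subgroups of a Phase 2b dose-ranging trial. It is prespecified, and its name shows that the arms differ in ICS dose. That is fair on reach: nothing in the primary or secondary analyses depends on it. It does not answer the point, because the other ICS-dose comparisons are randomized within a level and this one is not, and the SAP does not say so.

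Four stronger readings are tempting, and the documents do not support them.

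- *That the sponsor plans an ICS-sparing claim.* Neither document states such an objective, endpoint or claim. It is a possible misreading of the result.
- *That the bias favours GB001 because high-dose subjects are sicker.* The documents do not say which stratum has the higher risk of worsening. The effect of the ICS dose itself is also in the contrast. The bias could go either way.
- *That 12% and 25% are the error rates of the planned analysis.* They come from an unadjusted test on assumed risks. The SAP model adjusts for two measures of asthma status, which may reduce the figures by an amount that cannot be calculated here.
- *That the SAP promises this contrast its own p-value and forest-plot row.* Section 8.4 expressly promises interaction p-values and forest plots of the subgroup effects. A modelled estimate is likely because the main models are reused, but separate reporting is inferred.

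**Conclusion.** The concern holds in a limited form. The crossed contrast is not protected by randomization, the SAP attaches no caveat to it, and the planned adjustment cannot be shown to remove the confounding. That conclusion follows from the design and needs no assumption about rates.

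Its size does rest on assumptions. A modest stratum difference, 22% against 28%, is enough in an unadjusted test to raise the chance of a nominally favourable result with an inert drug from 2.6% to about 12% for one dose. The opposite difference lowers it to 0.3 to 0.4% and can conceal benefit. The contrast would be unbiased for the drug effect only if no residual difference remained between the strata, and this design cannot establish that.

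The primary and secondary analyses, the comparisons within each ICS stratum and the interaction test are unaffected.

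**What to change.** Remove the crossed contrast from the treatment-effect subgroup analyses and forest plots in SAP 8.4. Base inference on ICS dose on each GB001 dose against placebo within the medium and within the high stratum, together with the treatment-by-ICS interaction.

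If the sponsor wants to keep the contrast, state its purpose, present it apart from the randomized subgroup effects, label it descriptive and non-randomized, and report no p-value. A confidence interval to show imprecision is acceptable.

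The cost is a wording change in the SAP and the loss of one exploratory inferential comparison. No randomized information is given up.

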5.3. Randomization Criteria

At the end of the Run-in period, study subjects must fulfill the following criteria to be randomized to study treatment:

1. **Eosinophilic asthma:** A peripheral blood eosinophil count of ≥ 250 cells/ μ L measured at the Screening visit. **NOTE:** In a subject with prior evidence of an eosinophilic phenotype, as assessed by the Investigator, an eosinophil count < 250 may be repeated during Run-in upon approval by the Medical Monitor.
2. **FEV₁:** The morning percent predicted FEV₁ must be $\leq 85\%$ of the predicted normal at both the Screening visit and Randomization visit.
3. **FEV₁ overread:** The Screening visit overread by vendor must confirm eligibility was met.
4. **eDiary compliance:** Compliance with completion of the eDiary as defined as:
 - Completion of rescue medication use question on 4 or more of the last 7 days immediately prior to Visit 2 (includes the morning of Visit 2).

AND

- Completion of AM PEF on 4 or more of the last 7 mornings immediately prior to Visit 2 (includes the morning of Visit 2).
 - **Note:** If the eDiary was completed on < 4 days due to technical challenges, the Visit 2 may be delayed up to an additional 3 days to allow for completion of the eDiary parameters above.
5. **ACQ-5:** The ACQ-5 assessment has been completed in the eDiary in clinic during the Randomization visit.
 6. **Laboratory abnormality:** No evidence of clinically significant abnormality in the hematological, biochemical, or urinalysis at Screening visit, as judged by the Investigator.
 7. **Hepatitis status:** No evidence of chronic hepatitis B or C, as evidenced by a negative hepatitis B surface antigen (HbsAg) or hepatitis C test at the Screening visit. Note: if hepatitis C antibody test is positive or indeterminate at screening, the confirmatory test result must be negative for Hepatitis C.
 8. Chemistry and hematology obtained at Screening visit:
 - ALT must be $< 2x$ the upper limit of normal (ULN)
 - AST must be $< 2x$ ULN
 - Alkaline phosphatase must be $< 2x$ ULN
 - Bilirubin must be $< 1x$ ULN
 - Absolute eosinophil count must be $< 1,500$ cells/ μ L
 - White blood cell count must be $< 15,000$ cells/ μ L

9. **ECG overread:** The screening ECG overread confirms the QTcF interval is < 450 msec for males or QTcF < 470 msec for females.

10. **Asthma exacerbation:**

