2.5. Sample Size Determination

A total sample size of approximately 480 subjects (approximately 120 per treatment group, randomized in a 1:1:1:1 ratio) is estimated to provide 80% power to detect a reduction in odds of 66% between each GB001 group and placebo at an 0.050 two-sided level of significance for the primary endpoint of the proportion of subjects who experience worsening of asthma by Week 24. This assumes the proportion of subjects who experience worsening of asthma by Week 24 is 25% in the placebo group and 10.2% in each GB001 group and a dropout rate of 8%.

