3. GENERAL ANALYSIS AND REPORTING CONVENTIONS

All analyses will be performed using SAS® System (SAS Institute Inc., Cary, NC) version 9.4 or later.

Categorical variables will be summarized using counts (n) and percentages (%) and will be presented in the format "n (xx.x)". If a count is 0, no percentage will be shown. To ensure completeness, summaries for categorical and discrete variables may include all categories, even if no subjects had a value in a particular category. Additionally, for missing data, a category of "Missing" will be presented as needed.

Continuous (cts) variables, unless otherwise stated, will be summarized using descriptive statistics: number of subjects with non-missing data (n), mean, standard deviation (SD), median, 25th and 75th percentiles, minimum, and maximum. Descriptive statistics on select measures may also include the standard error (SE). Rounding rules for reporting cts descriptive summary statistics are as follows:

- If the original values have 0 or 1 decimal places: mean, median, 25th and 75th percentiles will be reported to one more decimal place than the original values, and SD and SE will be reported to 2 more decimal places than the original values
- If the original values have 2 or more decimal places: mean, median, 25th and 75th percentiles, SD, and SE will all be reported to 3 decimal places

Minimum and maximum will always be reported to the same decimal places as the original values, up to a maximum of 3 decimal places.

Efficacy results will be summarized by various measures including but not limited to odds ratios (ORs), hazard ratios, rate ratios, least squares (LS) means, differences in LS means, SEs, p-values, and two-sided confidence intervals (CIs). The ORs, hazard ratios, rate ratios, and corresponding CIs will be reported to 3 decimal places, percentage reductions and corresponding CIs will be reported to 1 decimal place, and SEs, LS means, differences in LS means and corresponding CIs will be reported per the rules above. P-values will be reported to 4 decimal places, with values less than 0.0001 displayed as < 0.0001 and values greater than 0.9999 displayed as > 0.9999. All statistical hypothesis tests will be two-sided with a significance level of 0.050.

Values with "<" or ">" signs will be analyzed without the signs in tables and figures. In bysubject data listings, values will be reported as collected with the sign.

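### SAP 8.4 tests eosinophils and FeNO as predictors of response only through separate cut-offs; adding a continuous-marker interaction would recover power if the relation is graded

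*SAP*

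**What the plan says.** SAP 8.4 lists the biomarker subgroups for the primary endpoint, ACQ-5 and pre-bronchodilator FEV₁, with some also used for the severe exacerbation rate.

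- Eosinophils are split three ways: "Blood eosinophils at Baseline (GI/L; < 0.20, ≥ 0.20; < 0.25, ≥ 0.25 [including for annualized rate of severe asthma exacerbations", and again at 0.30 GI/L.
- FeNO is split four ways: "FeNO at Baseline (ppb; < 25, ≥ 25 [including for annualized rate of severe asthma exacerbations", and again at 30, 35 and 50 ppb.
- Four two-level groupings combine 0.25 GI/L with each FeNO cut, and one four-level grouping crosses 0.25 GI/L with 25 ppb.

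The stated test is categorical: "Heterogeneity of treatment effect across different levels of each subgroup will be evaluated by presenting p-values for the treatment by subgroup interaction". SAP 3 sets the level: "All statistical hypothesis tests will be two-sided with a significance level of 0.050". SAP 8.1.3 applies no general multiplicity adjustment. SAP 8.4 does not fit models to any subgroup level holding less than 10% of the ITT population.

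The subgroups use the Baseline value, which SAP 3 defines as the last one on or before first dose. Entry uses a different measurement. Protocol 5.3 requires "A peripheral blood eosinophil count of" at least 250 cells/µL at Screening, or on a repeat approved by the Medical Monitor. FeNO has no entry threshold.

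Elsewhere the markers appear as continuous variables only in the baseline summaries (SAP 6.5) and, for FeNO, as a covariate in the model of FeNO change (SAP 8.3.3.3.1). Neither addresses prediction of response.

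**The concern.** The programme targets an eosinophilic phenotype, and Protocol 2.2 supports it with a post-hoc reading of 36 subjects by FeNO (14 in the high group) and eosinophils (16 in the high group). A trial of about 480 subjects is a far better place to learn whether response rises with either marker.

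A split discards the ordering within each side. If the relation is graded, the planned tests are weaker than the data allow. Several correlated p-values also answer one question, and no cut-off is named as the main one. For eosinophils there is a further difficulty: after selection at 250 cells/µL, the groups below 0.20 and 0.25 GI/L depend largely on visit-to-visit change, and they may be small.

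**Working it through.** **The plan's own power figure.** SAP 2.5 says that the sample "is estimated to provide 80% power to detect a reduction in odds of 66% between each GB001 group and placebo", with "approximately 120 per treatment group, randomized in a 1:1:1:1 ratio". It assumes that the event proportion "is 25% in the placebo group and 10.2% in each GB001 group and a dropout rate of 8"%.

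- Evaluable per arm: 120 × 0.92 = 110.4.
- Odds ratio: (0.102/0.898)/(0.25/0.75) = 0.341, a 66% reduction; |ln OR| = 1.077.
- SE = √[1/27.6 + 1/82.8 + 1/11.26 + 1/99.14] = 0.384.
- Power = Φ(1.077/0.384 − 1.96) = 80.1%.

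The stated 80% is reproduced for the main comparison. The documents give no power for any subgroup interaction, so the rest is conditional.

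**Information kept by one split.** Assume a marker that is normal on the log scale and a treatment effect linear in it. A split with share q on one side keeps r = φ(z_q)²/[q(1−q)] of the interaction information. A test with 80% power on the continuous marker then has power Φ[(1.960 + 0.842)√r − 1.960].

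| Split | φ(z_q) | Kept r | Lost | Equivalent N of 480 | Power |
|---|---|---|---|---|---|
| 50/50 | 0.399 | 0.637 | 36% | 306 | 61% |
| 25/75 | 0.318 | 0.539 | 46% | 259 | 54% |
| 20/80 | 0.280 | 0.490 | 51% | 235 | 50% |
| 10/90 | 0.175 | 0.342 | 66% | 164 | 37% |

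The last row is the most uneven two-level split that the SAP's 10% rule lets through.

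**The actual cut-offs.** These are simulated, and all distributions are assumed.

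- Eosinophils (geometric mean 200–280 cells/µL, log SD 0.5–0.7, Screening–Baseline correlation 0.5–0.85, selected at 250 or above and below 1,500 at Screening): the share below 0.20 GI/L is 4–29%, and below 0.25 GI/L 15–46%. The loss is 43–84% at 0.20, 37–63% at 0.25 and 36–48% at 0.30. In 4 of the 12 scenarios the group below 0.20 is under 10% and would not be modelled; in the other eight the loss at 0.20 is 43–69%.
- FeNO (geometric mean 20–40 ppb, log SD 0.6–0.8): the loss is 36–61% wherever both sides reach 10%.

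**Binary endpoint.** A logistic simulation used four arms of 110, an assumed log-odds-ratio change of −0.8 per SD of the marker, a 3-df likelihood-ratio test and 1,500 trials per setting. Power was 63–66% with the continuous marker, against 47% (50/50), 40% (25/75) and 29% (10/90). With no interaction, rejection was 5–6% for the continuous test and 6–8% for the split, so the split figures are if anything flattered.

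**Number of tests.** There are 3 + 4 + 4 + 1 = 12 eosinophil/FeNO groupings. Three endpoints give 36 analyses, and four groupings repeated for the exacerbation rate make 40. With no true interaction (one dose versus placebo, 110 per arm, continuous outcome, assumed FeNO median 28 ppb and log SD 0.7), at least one of the four FeNO cuts reached p < 0.05 in 13% of simulated trials, against 5% for one continuous test.

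**The reverse case.** If response steps at the cut, the same r is what a linear term keeps. A split test with 80% power would then correspond to about 61% (50/50) or 50% (20/80) for the linear term.

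**The case against.** The strongest reply is that the loss depends on shape. A reader might infer that the plan simply throws away a third to two thirds of the information. The documents do not support that, because they give no shape for the relation, and a true step at a cut-off reverses the comparison. For the same reason they do not support replacing the cut-offs by a linear test. This part of the objection stands in full.

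The cut-offs are not arbitrary either. Protocol 2.2 shows that the earlier 28-day data were analysed at FeNO 35 ppb and eosinophils 200/µL, which SAP 8.4 repeats, and 0.25 GI/L matches entry. The multiple FeNO cuts also recover some ordering: a split at 25 ppb puts 26 and 200 ppb together, but the 30, 35 and 50 ppb splits separate them. Fitted jointly, the cuts would lose less (about 16–31% for the four FeNO cuts and 19–43% for the three eosinophil cuts, under the distributions above). The SAP, however, tests each one separately.

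The planners saw the small-group problem: the 10% rule covers it, and SAP 6.5 tabulates qualifying against baseline eosinophils. Power should not be quoted for a 0.20 GI/L test in scenarios where that rule would bar it.

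Finally, this is exploratory work. Protocol 9.4.3 allows biomarker analyses in a separate SAP that is not among the documents, and some protocol text is redacted. It cannot be said that no continuous model exists in the programme, only that this SAP, which defines the heterogeneity test for these endpoints, has none.

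**Conclusion.** The point holds as a low-cost improvement and not as an error in the plan. SAP 8.4 examines both markers only through categories, each with an unadjusted p-value, and two of the three eosinophil cuts sit at or below the entry threshold. Under a relation roughly linear in the log marker, the information loss per split is about 36–66%, and 80% power becomes about 61–37%. Both ranges rest on that assumed shape and on an approximately normal log marker; at a true step, a split there loses little. The primary and secondary treatment comparisons are unaffected.

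**What to change.** In SAP 8.4, for the primary endpoint, ACQ-5, pre-bronchodilator FEV₁ and the severe exacerbation rate, pre-specify one model for baseline eosinophils and one for baseline FeNO. Each takes the endpoint's planned model (SAP 8.3.1, 8.3.2.1 or 8.3.2.3) and adds log2(marker) and a treatment-by-log2(marker) interaction. Check linearity with a spline term, and plot the treatment effect with its 95% CI across the observed range.

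Report these models alongside the planned cut-off analyses. All of the cut-offs stay, including those that repeat the earlier 28-day cuts.

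The cost is a paragraph of SAP text and eight exploratory models (two markers × four endpoints), plus spline checks, on data already collected. The downside is a few more exploratory p-values, and a linear term that has less power than a split if the true relation is a step. Keeping both analyses covers that case.
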